7.2.3 Number of Subjects Required

Thirty subjects are to be enrolled in the investigation, i.e. will receive the implant.

It is expected that approximately 33 subjects are to be screened to meet this sample size.

7.2.4 Vulnerable Populations

Not applicable.

7.2.5 Enrolment & Investigation Duration

The following subject status definitions apply:

Screened: A consented subject who is being assessed for eligibility according to the Screening requirements.

Screen Fail: A consented subject that has been determined to not meet all eligibility criteria for enrolment.

Enrolled: Subjects who have met all eligibility criteria and have received the implant.

If a subject discontinues his/her participation in the investigation, he/she will not be replaced if this discontinuation occurs after surgery is performed. If this discontinuation occurs before surgery the subject will be replaced in order to reach 30 evaluable subjects.

The enrolment period for the investigation is anticipated to be approximately 4 - 6 months from the time of first subject consent to enrolment of the last subject.

The expected duration of each subject's participation in the investigation, is 6 months from surgery.

The anticipated total duration of the clinical investigation is maximum 12 - 15 months.

Completion of investigation is defined as last subject last visit. In the event of an ongoing SADEs at the time of this last visit, the investigation completion will be extended for a further 30 days, or until resolution or stabilisation of the event, whichever comes first.

7.2.6 Criteria for Subject Withdrawal

Subjects can decide to withdraw from the investigation at any time. The investigator shall ask for the reason(s). The reason for withdrawal should to be documented in the subject's source files and the CRF.

The investigator or Sponsor may also decide to withdraw a subject from the clinical study if it is considered to be in their best interests.

Subject withdrawal may be for any of the following reasons:

- Adverse Event (AE)
- Device Deficiency (DD)
- Repeated and severe CIP or GCP deviation
- Subject lost to follow-up
- Subject withdrew consent

- Subject death
- Sponsor decision
- Investigator decision
- Other (specify)

If subject withdrawal is due to problems related to the Investigational device, safety or performance, the investigator shall ask for the subject's permission to continue in safety follow up (i.e. adverse events) until their scheduled final study visit.

If a subject is lost to follow-up, every possible effort must be made by the study site personnel to contact the subject and determine the reason for discontinuation. At least three separate attempts taken to contact the subject must be documented.

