9.5 Analysis Populations

The final definition of the analysis sets (ITT, PP and Safety) will be taken at the clean file meeting before database lock.

- The Intention-to-Treat population (ITT) will include all subjects who have undergone surgical intervention.
- The Per Protocol population (PP) will include subjects that have completed the study according to the protocol. Subjects that were incorrectly included or were considered major protocol violators that affect the primary analysis should be removed from the PP population.
- The Safety population consists of all surgically treated subjects

All efficacy analyses will be performed on both ITT and PP populations.

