### **3.4 Additional Statistical Considerations**

#### **3.4.1 Missing, Unused or Spurious Data**

All ITT analyses will be performed/presented both for the imputed (main analyses) and for the non-imputed data (sensitivity analyses).

Imputation of missing values will be performed for all efficacy variables. No imputation of baseline values or baseline carry forward will be made. Imputations will be made according to the following rules:

1. If a value is missing at the end of a time period for a patient, last observation will be carried forward.
2. If a missing value is occurring between two time points with values, an interpolation will be made for continuous variables and for categorical variables the value from the previous visit will be carried forward.
3. As a sensitivity analysis imputation of missing values will be performed for all efficacy variables using stochastic regression imputations.

Spurious data will be cleaned prior to clean file meeting. If spurious data are detected after clean file is declared actions to consider will be;

1. unlock, correction of the spurious data and a new re-lock will be made alternatively,
2. a sensitivity analysis will be performed that accounts for the spurious data in a proper statistical fashion (e.g. non parametric methods).

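### Implanted subjects withdrawn under section 7.2.6 are asked for adverse-event follow-up at most, so ITT can lack their 3- and 6-month hearing and questionnaire results

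*Protocol*

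**What the plan says.** Protocol 7.2.6 gives the power to withdraw in these words: "The investigator or Sponsor may also decide to withdraw a subject from the clinical study if it is considered to be in their best interests". The list of reasons that follows contains events that necessarily end data collection (death, loss to follow-up, withdrawn consent). It also contains events that need not: adverse event, device deficiency, "Repeated and severe CIP or GCP deviation", "Sponsor decision" and "Investigator decision".

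Continued follow-up is requested only when the withdrawal stems from device, safety or performance problems. The subject is then asked for permission to "continue in safety follow up (i.e. adverse events) until their scheduled final study visit". After withdrawal for a deviation, or for a sponsor or investigator decision unrelated to such problems, nothing further is requested.

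On the analysis side, Protocol 9.5 states: "The Intention-to-Treat population (ITT) will include all subjects who have undergone surgical intervention". SAP 3.3.2 agrees. Protocol 7.2.5 does not replace subjects who discontinue after surgery. The main efficacy analysis is ITT at 3 months (Protocol 9.1, SAP 3.2.5). SAP 3.4.1 makes last observation carried forward the rule for a value missing at the end of a period, and adds: "No imputation of baseline values or baseline carry forward will be made". Stochastic regression imputation is a sensitivity analysis there, and a non-imputed analysis is also presented.

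**The concern.** The analysis set and the data-collection rule pull apart. ITT promises to represent every operated subject, but the plan makes no arrangement to obtain the 3-month result from a subject who is withdrawn while still willing to be tested. Per protocol cannot represent that subject either, because it requires completion of the study.

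The trial is open and single-arm, so whoever decides on withdrawal may know how the subject is doing, and no control arm offsets the resulting selection. If withdrawn subjects tend to have the poorer results, the ITT means lean towards those who stayed. Ending data collection on deviators also gains nothing analytically. Per protocol already removes major violators, and Protocol section 13 excludes data from the per-protocol group only, even after gross misconduct.

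**Working it through.** **1. What the main analysis holds for a subject withdrawn before 3 months** (schedule of events; Protocol 7.3.2.2 and 7.3.2.3; SAP 3.4.1)

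| Outcome (hierarchy step) | Post-baseline visits | Value used at 3 months |
|---|---|---|
| PTA4 (1), SNR (2), speech in quiet at 65 dB (3) | Fitting (4 weeks), 3M, 6M | Fitting value carried forward; none if withdrawn before fitting |
| APHAB (4), HUI hearing attribute (5), SSQ (6) | 3M, 6M | None: nothing after baseline to carry, and baseline may not be carried |

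A withdrawal after the 3-month visit affects only the 6-month data.

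**2. The plan's own power figures.** Inputs from Protocol 9.4 and SAP 3.1: PTA4 change −25 dB, SD 9.5; SNR change −7.6 dB, SD 8.1; n = 30; two-sided alpha 0.05. I used the paired t-test (noncentral t, df = n − 1) as a proxy for the permutation test.

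- PTA4: noncentrality 25/9.5 × √30 = 14.4, power above 0.999.
- SNR: noncentrality 7.6/8.1 × √30 = 5.14, power 0.9987.

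Both agree with the stated 0.99. If subjects are simply lost, SNR power is 0.998 at n = 29 and at n = 28, and it stays at or above 0.90 down to n = 14.

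**3. Questionnaires.** Assume k of 30 are withdrawn before 3 months with no true change, and the rest have mean change Δ. The reported mean is Δ; the mean over all operated subjects is Δ(30 − k)/30. Relative inflation = 30/(30 − k) − 1.

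- k = 1: 30/29 − 1 = 3.4%.
- k = 2: 30/28 − 1 = 7.1%.

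**4. PTA4 and SNR.** Assume the carried-forward fitting value equals the planned change and the true 3-month change is between half of it and zero. The overstatement is k/30 times the shortfall.

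- PTA4, k = 1: 12.5/30 to 25/30 = 0.42 to 0.83 dB. k = 2: 0.83 to 1.67 dB. The SE of the mean is 9.5/√30 = 1.73 dB.
- SNR, k = 1: 3.8/30 to 7.6/30 = 0.13 to 0.25 dB. k = 2: 0.25 to 0.51 dB. The SE is 8.1/√30 = 1.48 dB.

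**5. How large might k be?** The documents give no withdrawal rate. Protocol 4.2.2.1 reports that all 51 predecessor subjects passed the 6-month follow-up and so completed the 3-month efficacy endpoint. Read as 0 of 51 lost, the one-sided 95% upper bound is 1 − 0.05^(1/51) = 5.7%, and 30 × 0.057 = 1.7 subjects. Hence k = 1 or 2 is used above.

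**The case against.** **Withdrawals will be rare.** This stands as to size. A reader might infer from the 71 device deficiencies in 51 predecessor subjects (Protocol 4.2.2.1.2) that the grounds for withdrawal will arise often. The documents do not support that. None of the 71 concerned the implant; most concerned fitting software or the sound processor. The same 51 subjects are reported as having passed 6 months. A deficiency count is not a withdrawal rate.

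**Withdrawal is conditioned on the subject's best interests.** This also stands. The list can be read as reason codes for the CRF, so 7.2.6 should not be taken as giving the sponsor or investigator a free hand to remove poor performers. The condition does not supply the missing results, however.

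**Sensitivity analyses exist.** Stochastic regression covers all efficacy variables, questionnaires included, and a disposition table is planned. This softens the point. But the imputation must borrow from subjects who stayed, and it is not the main analysis.

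**The text does not forbid later testing.** True; it is silent. The gap is that nobody is told to ask.

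**Collecting the data would not protect power.** Correct, although a reader might infer that it would. Assume an HUI effect of d = 0.474 (predecessor p = 0.0014, n = 51 assumed). Paired t-test power is then 0.71 at n = 30 and 0.68 at n = 28. If the two missing subjects had no benefit and were tested, d falls to about 0.44 (mean 0.474 × 28/30, slightly larger SD) and power to about 0.64. The reason to collect is representativeness.

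**Off-device tests measure something else.** This stands and shapes the fix. Protocol 9.2.1 defines the outcome as hearing when using the device.

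**Conclusion.** The point holds as a gap in data collection. A subject withdrawn before 3 months stays in ITT, but with a 4-week hearing value at best and no main-analysis value for steps 4 to 6.

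The likely size is small. One or two such subjects of 30 would inflate a questionnaire mean change by 3.4% or 7.1% if they had no benefit. They would overstate PTA4 by at most about 0.8 or 1.7 dB under the assumptions in step 4. Both the number withdrawn and their outcomes are assumptions. The predecessor experience is compatible with none, although its wording could also mean only that the visit date had passed.

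A reader might go further and infer that the primary conclusion or its power is in danger. The documents do not support that: PTA4 power is near 1, and SNR power is 0.998 with two subjects lost. The change is worth making because it is cheap and because a 3-month result not collected at the time cannot be recovered afterwards.

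**What to change.** In Protocol 7.2.6, separate stopping device use or deviating from the protocol from leaving the study. Widen the existing permission request beyond adverse events. Implanted subjects who have not withdrawn consent would be asked to attend the scheduled 3- and 6-month hearing tests and questionnaires, unless the investigator judges further testing not to be in the subject's interest. Device use would be recorded at each visit. This is a rule on data collection only; it says nothing on when device use should stop.

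In SAP 3.4.1, state that on-device values observed after such an event enter ITT in place of carried-forward values, and that deviators are handled through the per-protocol set. Report results from subjects no longer using the device separately or as a sensitivity analysis, so that the outcome in Protocol 9.2.1 is not redefined.

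The cost is a short paragraph in 7.2.6, a few lines in the SAP, and a few follow-up visits for subjects who would otherwise have left. The visits and tests are already in the schedule.

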4.2.2.1.2 Safety

In total 68 *Adverse Events* (AEs) were reported during the first six months of the clinical investigation, whereof thirty-three (33) were judged as possibly, probably or causally related to the study device and/or procedure. Most of the AEs were reported as mild and related to post-operative pain or transient irritation/swelling.

Three (3) *Serious Adverse Events* (SAEs) were reported within the first six months and within the same subject. Two (2) of these SAEs were unrelated to the study device and/or procedure, and one (1) was related to the surgical procedure: One Osia Implant was removed due to wound infection starting shortly after surgery. There were no device-related SAEs recorded during this time period.

Seventy-one (71) *Device Deficiencies* (DDs) have been reported (to date); However, none of the DDs were related to the Implant (Fitting Software: 46.5%; Sound Processor: 41%; User Manual: 8.5%; Broken safety line: 4%)

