11.2 Recording and Handling of Adverse Events

Subjects shall be carefully monitored during the clinical investigation and the investigator should enquire about AEs at each visit.

All AEs will be recorded from Screening/Baseline. AE recording will continue for each subject until completion of the final visit. Ongoing SAEs, SADEs and/or AESI will be followed for 30 days, or until resolution or stabilisation of the event, whichever comes first.

Source notes should indicate the evaluation for AEs, even if none to report. All required AEs will be reported if observed, even if anticipated and/or acknowledged as a risk factor in the consent.

All AEs will have the following information documented: start and stop dates, action taken, outcome, severity and investigators opinion on the potential relationship to the Investigational device and investigational procedures. If an AE changes in severity, the most severe (highest) grade will be captured for that event on the Adverse Events CRF.

Adverse events will be summarized by CTCAE to System Organ Class (SOC) and CTCAE term.

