#### **3.4.4.14 Adverse events**

Separate tabulations of AEs, ADEs, SAEs, SADEs and AESIs will be produced. AEs, ADEs and AESIs will also be produced by severity (mild, moderate or severe) and relationship (related defined as Possibly, Probably and Definitely related). Number of events, number of subject and percent with events by System Organ Class (SOC, CTCAE) and CTCAE term will be presented.

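### Only implanted subjects who withdraw for device, safety or performance reasons are asked to stay in adverse-event follow-up, so collection may stop early for others; separately, two sections list different events to follow past the last visit

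*Protocol*

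**What the plan says.** **Withdrawal.** Protocol 7.2.6 lists nine possible reasons for withdrawal, among them "Repeated and severe CIP or GCP deviation", sponsor decision, investigator decision and a free-text category. It then sets a condition, "If subject withdrawal is due to problems related to the Investigational device, safety or performance", and under that condition "the investigator shall ask for the subject's permission to continue in safety follow up (i.e. adverse events) until their scheduled final study visit". There is no matching instruction for the other reasons.

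**General recording rule.** Protocol 11.2 states: "AE recording will continue for each subject until completion of the final visit". Section 7.4 speaks of reporting all events up to the last visit of the last subject.

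**Who is counted.** Protocol 7.2.5 does not replace subjects who leave after surgery. Protocol 9.5 and SAP 3.3.1 put everyone who had surgery in the Safety population. SAP 3.4.4.14 reports "Number of events, number of subject and percent with events by System Organ Class (SOC, CTCAE) and CTCAE term".

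**Events still ongoing at the end.** Protocol 7.2.5: "In the event of an ongoing SADEs at the time of this last visit, the investigation completion will be extended", by up to 30 days. Protocol 11.2: "Ongoing SAEs, SADEs and/or AESI will be followed for 30 days, or until resolution or stabilisation of the event", whichever comes first.

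**The concern.** A subject who leaves the study after surgery still has the device in place and can still have an implant-site or device event. Under 7.2.6, whether anyone asks that subject to remain in adverse-event follow-up depends on the reason recorded for leaving. A site that follows the section literally asks some subjects and not others.

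The analysis does not adjust for this. The percentage with an event is taken over all implanted subjects, so a subject who is no longer observed counts as event-free from that point. The error can only go one way: it lowers the reported percentage. In a pre-market implant study of 30 subjects with no independent data monitoring committee (Protocol 11.5), a few unobserved subjects matter to the safety summary.

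The end-of-study issue is separate. If the study is formally complete under one section while another still requires follow-up of an event, it is unclear whether the outcome of that event will reach the final report.

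**Working it through.** **Step 1. Which reasons trigger the request in 7.2.6?**

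| Reason listed in 7.2.6 | Covered by the request? |
|---|---|
| Adverse event; device deficiency | Largely yes |
| Death | Not applicable |
| Lost to follow-up | Separate rule: three documented contact attempts |
| Consent withdrawn | Only if attributed to the device, safety or performance; the subject may refuse |
| Protocol or GCP deviation | No |
| Sponsor decision; investigator decision | Only if the cause is the device, safety or performance |
| Other | Only if the cause is the device, safety or performance |

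**Step 2. Does 11.2 fill the gap?** It runs recording to each subject's final visit. Protocol 14 defines a withdrawn subject as one who leaves before the expected last visit, so such a subject may have no final visit. Section 7.2.6 treats further follow-up as needing permission and directs that it be sought in one situation only. Read together, the sections leave the other withdrawals undetermined.

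**Step 3. Reproduce the plan's exposure figure.** Inputs from Protocol 9.4: 30 subjects, 3 months. Patient-years = N × months / 12 = 30 × 3 / 12 = 7.5, as stated. At 6 months, 30 × 6 / 12 = 15.0. Both assume that nobody is lost after surgery.

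**Step 4. Effect on a percentage.** One missed subject with an event: 1/30 = 3.3 points. If m subjects are unobserved, the largest possible understatement is m/30.

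**Step 5. Range under assumed losses.** The documents give no post-surgery dropout rate, so m is an assumption. Exposure if the m subjects leave right after surgery is (30 − m) × T / 12. If they leave midway it is 30 × T / 12 − m × T / 24.

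| m | Patient-years at 3 months (at once / midway) | Patient-years at 6 months (at once / midway) | Largest understatement, m/30 |
|---|---|---|---|
| 0 | 7.5 / 7.5 | 15.0 / 15.0 | 0 |
| 1 | 7.25 / 7.375 | 14.5 / 14.75 | 3.3 points |
| 3 | 6.75 / 7.125 | 13.5 / 14.25 | 10 points |
| 6 | 6.0 / 6.75 | 12.0 / 13.5 | 20 points |

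The last column is a ceiling: it needs every unobserved subject to have an event of the same type after leaving.

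**Step 6. Chance of seeing an event at all.** For an assumed true risk of 5%, the chance of at least one affected subject among n fully followed is 1 − 0.95^n. This gives 0.785 for n = 30, 0.774 for 29, 0.750 for 27 and 0.708 for 24.

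**Step 7. Events ongoing at the end.** Section 7.2.5 names serious adverse device effects only. Section 11.2 names serious adverse events, serious adverse device effects and events of special interest. Section 11.1.6 counts as of special interest an implant-site event that leads to an antibiotic prescription. Such an event need not be serious, and a non-serious event cannot be a serious device effect under 11.1.4. If one is ongoing at the last visit of the last subject, 11.2 requires follow-up while 7.2.5 does not extend the study.

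**The case against.** **The plan does not say that collection stops.** This is right. Section 7.2.6 is silent on the other reasons, and 7.4 and 11.2 point towards continued recording. A reader might infer from 7.2.6 that safety data do stop for all other withdrawals. The documents do not support that: the most that can be said is that they may stop, depending on how a site reads three sections together. Nor do the sections flatly contradict each other on withdrawals.

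**The group is small, and the subjects most likely to have device events are already asked.** This largely stands. Protocol 4.2.2.1 reports that all 51 predecessor subjects passed their 6-month follow-up, which suggests low loss. It does not give a dropout rate for this study.

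**Losses would be partly visible.** Also fair. Events before withdrawal still count, SAP Table 14.1.1 covers disposition, and device exposure is collected (Protocol 7.3.2.5). However, the SAP's table list has no exposure or safety follow-up table, and nothing requires incomplete follow-up to be shown beside the event percentages.

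**Sections 7.2.5 and 11.2 govern different things.** One sets when the investigation is complete, the other how long an event is followed, and a site could obey both. The mismatch covers at most 30 days and does not shorten data for withdrawn subjects. The lists still differ.

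Two further inferences should be resisted:

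- With accrual over 4 to 6 months, assumed even, 1/6 to 1/4 of subjects (17% to 25%, or 5 to 7.5 of 30) have a last visit in the final month. That is not the share affected, because a subject must also have a relevant event ongoing. In the predecessor study 1 of 51 subjects had serious events by 6 months; 5/51 to 7.5/51 is about 0.10 to 0.15 subjects, even if every such event were still ongoing. No rate is given for events of special interest.
- The predecessor case, "One Osia Implant was removed due to wound infection starting shortly after surgery", might seem to be a serious event that falls outside 7.2.5. Its class is unsettled: 4.2.2.1.2 calls it procedure-related and reports no device-related serious events, while 8.2 lists it among adverse device effects and 11.1.2 brings inadequacies of implantation into that term. It also began soon after surgery. The antibiotic example in Step 7 does not depend on it.

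**Conclusion.** The point holds in a limited form. The request for continued adverse-event follow-up is tied to the stated reason for withdrawal, and no section extends it to the remaining reasons. Followed literally, the rule can lose safety data on people who still carry the implant and are counted as event-free, so event percentages could be too low.

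The firm size is 3.3 points for each missed subject with an event. The total cannot be computed from the documents. The exposure figures and detection chances above illustrate assumed losses of 1, 3 or 6 subjects and predict nothing. The conclusion assumes that some withdrawals for other reasons occur after surgery and that some of those subjects would agree to stay in follow-up if asked.

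The difference between 7.2.5 and 11.2 is a separate and smaller matter. It is a genuine inconsistency in the listed events, limited to non-serious-device-effect events still ongoing around the end of the study.

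**What to change.** 1. **Protocol 7.2.6:** have the investigator ask every implanted subject who stops, whatever the reason, for permission to continue adverse-event collection to the scheduled final visit, by telephone where a visit is not possible. A subject remains free to refuse.
2. **SAP 3.4.4.14:** report the number of subjects with incomplete safety follow-up beside the event percentages.
3. **Protocol 7.2.5 and 11.2:** reconcile the two so that one list of event types governs follow-up past the last visit. Which list applies is for the sponsor and investigators to decide.

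The cost of items 1 and 2 is a wording change, a check that the consent form allows the contact, a few telephone contacts and one line in the SAP. Item 3 is wording, although the study could stay open up to 30 days longer if the wider list is adopted.
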